## GLOSSARY OF ABBREVIATIONS

AES	Advanced Encryption Standard
BASEC	Business Administration System for Ethical Committees
CRF	case report form
Ct	cycle threshold
EBPI	Institut für Epidemiologie, Biostatistik und Prävention
FOPH	Federal Office of Public Health
GSS	guided self-sampling
H0	null hypothesis
H1	alternative hypothesis
HCP	healthcare professional
HRA	Human Research Act
HRO	Ordinance on Human
NP	nasopharyngeal
OP+N	oropharyngeal and nasal
PCR	polymerase chain reaction
RT	realtime
SD	standard deviation
SOP	standard operating procedure
TLS	Transport Layer Security
USS	unsupervised self sampling
VOC	variant of concern
μs	mean in the standard treatment group
μe	mean in the experimental treatment group
d	non-inferiority limit

## 1 BACKGROUND AND PROJECT RATIONALE

The Severe Acute Respiratory Syndrome Coronavirus 2 (SARS-COV-2) pandemic has resulted in more than 3.8 billion registered tests, 275 million positive cases, and 5 million deaths worldwide. It will most likely remain for months or years. Early and regular testing has been an important pillar of secondary prevention, since the beginning. The current global emergence of the Omicron variant of concern (VOC), is rewriting the pandemic history because of the increased viral load and transmission. Current projections indicate that COVID-19 hospitalizations are likely to be higher in the next six months than in the last six months. Low vaccination rates foster new mutations and thus, reduce the effectiveness of vaccination. This puts older generations again at higher risk and shifts the timeline of the pandemic by at least several months.

As a consequence of the spreading of Omicron VOC, the 2G+ rule has been in effect in Switzerland, since December 20, 2021, meaning that in all publicly accessible cultural, sports, recreational, and entertainment areas, even double vaccinated and individuals who recovered more than four months ago are obliged to present a negative test, to be exempted from the mask requirement indoors. The new measures taken by Switzerland in response to the increasing number of omicron cases place an additional burden on the testing infrastructure, patience, and satisfaction of dually vaccinated, asymptomatic individuals as they adjust their daily lives as best they can to the circumstances with regular testing.

Regular testing is therefore expected to become a part of our lives to allow public operations. The testing infrastructure is currently costly to operate and maintain. In addition, the lack of availability of adequately trained personnel and insufficient accuracy and quality of testing urged some test centers to halt operations. This situation has exacerbated in decentralized, rural areas where the density of test centers results in longer travel distances and inherent transmission risks on public transport. However, this pandemic has also fostered solutions in the form of e telemedicine with enormously increased applicability, especially rural areas. Several emerging issues, such as the use of technology by older adults, the availability of high-capacity Internet access, and support for telemedicine, can be overcome in the near future to increase the benefits of telemedicine.

In Israel, the uptake of regular testing increased with the introduction of rapid home and self-testing. Especially in areas of high viral activity, self- and home-tested children allowed the schools to continue operating. Also, other Western countries, including the United Kingdom, the United States of America and Switzerland, introduced video-assisted sampling as a self-testing strategy. In Switzerland, this has been well received by broad segments of the

population; however, only polymerase chain reaction (PCR) tests had been medically approved to generate a certificate. The advantages are obvious: less exposure of symptomatic to healthy individuals in test centers, increased low-risk accessibility for e.g. immunocompromised people, consistent implementation of isolation and quarantine obligations without interruption for early termination based on negative testing. The available private information technology and communication infrastructure with smart devices reduce the provision of costly state infrastructure.

Studies comparing self-sampling were published, but none compared autonomous self-testing with guidance by healthcare specialists to sampling by healthcare professionals in a randomized controlled trial. Non-inferiority of oral + nasal vs. nasopharyngeal sampling has been proven. However, the question of whether telemedically supervised testing with SARS-CoV-2 Rapid Antigen Tests is non-inferior to the same tests being carried out by trained personnel in test centers is still open for debate.

With this study, we aim to compare and evaluate the reliability and sampling quality of self-performed rapid tests for professional use compared to professional sampling by healthcare personnel. This will be done by comparing cycle threshold (Ct) values of both housekeeping genes and SARS-CoV-2.

A solution that builds on the capacity of existing laboratories may be implemented with a high level of safety and minimizes the risk of transmission in rural areas. This fuels hope that medical personnel will be relieved of the burden of jointly managing the pandemic as a national and global challenge.

## 2.2 Primary and secondary endpoints

The Ct-value is defined as the number of cycles required for a signal to cross the detection threshold and can be used as a surrogate for sampling quality, as it allows to quantify the amount of material that is being extracted.

Primary endpoints:

- Concordance of positive/negative samples in antigen tests with GSS, USS, and HCP-based samples.

Secondary endpoints:

- Housekeeping gene Ct comparison based on sampling method between samples based on GSS, USS, or HCP
- ORF1ab/RdRp-, E-, N-, and S genes Ct value comparison based on sampling method between samples based on GSS, USS, or HCP
- Qualitative analysis of perceived sampling accuracy established with a short form
- Detected variant of concern
- Case report form (CRF) assessing basic demographics and variables of interests as indicated separately in the CRF form
- Prevalence of variants of concern
- Immunization status
- Travel destinations in the passed three months
- n of people in which a nasopharyngeal sampling is possible correctly (ratio)

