#### 4.1.2 Sample size

The SD of the mean of Ct values for RT-PCR analysis of multiple samples is not clearly defined in the literature and varies between studies.

If there is truly no difference between the standard and experimental treatment, then 85 patients per group are required to be 90% sure that the lower limit of a one-sided 97.5% confidence interval (or equivalently a 95% two-sided confidence interval) will be above the non-inferiority limit of -3.

We, therefore, estimated a standard error of six that accounts for this variance. In addition, the limit of non-inferiority was set at three according to clinical significance.

Results will be stratified by symptom status, age, and sex.

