### 4.1.3 Hypothesis

Primary outcome

*NP HCP vs OP+N HCP*

H0:  $\mu_e - \mu_s \leq -d \rightarrow \mu(\text{NP HCP ct}) - \mu(\text{OP+N HCP ct}) \leq -3$

H1:  $\mu_e - \mu_s > -d \rightarrow \mu(\text{NP HCP ct}) - \mu(\text{OP+N HCP ct}) > -3$

*OP+N HCP vs OP+N GSS*

H0:  $\mu_e - \mu_s \leq -d \rightarrow \mu(\text{OP+N HCP ct}) - \mu(\text{OP+N GSS ct}) \leq -3$

H1:  $\mu_e - \mu_s > -d \rightarrow \mu(\text{OP+N HCP ct}) - \mu(\text{OP+N GSS ct}) > -3$

*OP+N HCP vs OP+N USS*

H0:  $\mu_e - \mu_s \leq -d \rightarrow \mu(\text{OP+N HCP ct}) - \mu(\text{OP+N USS ct}) \leq -3$

H1:  $\mu_e - \mu_s > -d \rightarrow \mu(\text{OP+N HCP ct}) - \mu(\text{OP+N USS ct}) > -3$

Secondary outcome:

We will stratify the primary outcome by viral load (low, medium, high).

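### Section 2.2 makes antigen concordance the only primary endpoint, but the primary hypotheses, test and 90% power in section 4 are all for Ct, which 2.2 lists as secondary

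*Combined protocol and SAP*

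**What the plan says.** **Section 2.2.** The heading for primary endpoints is plural, but one bullet follows: "Concordance of positive/negative samples in antigen tests with GSS, USS, and HCP-based samples". The secondary list contains "Housekeeping gene Ct comparison based on sampling method between samples based on GSS, USS, or HCP" and "ORF1ab/RdRp-, E-, N-, and S genes Ct value comparison based on sampling method".

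**Section 4.1.3.** Three contrasts stand under the primary outcome: "NP HCP vs OP+N HCP", "OP+N HCP vs OP+N GSS" and HCP OP+N against USS. Each is written as a difference in mean Ct against -3. The secondary outcome there is a breakdown of the same quantity: "We will stratify the primary outcome by viral load (low, medium, high").

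**Section 4.1.2.** The text opens with the variability of Ct and states that "85 patients per group are required to be 90% sure" of excluding a limit of -3 with a one-sided 97.5% confidence interval when there is no true difference. On variability it says: "We, therefore, estimated a standard error of six that accounts for this variance".

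**Section 4.1.4.** A paired t or Wilcoxon non-inferiority test is planned for Ct, with Bland-Altman diagrams for agreement. Logistic regression is mentioned for confounders, with no outcome named.

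**Section 2.3.2.** Outside 2.2, concordance between GSS, USS and HCP sampling appears only here, as something to be assessed.

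**The concern.** The two parts of the plan name different primary outcomes. The endpoint that 2.2 calls primary has no rule for declaring success, and the outcome that has such a rule is called secondary in the same section.

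The two can disagree. A self-taken swab might yield a Ct within 3 cycles of the professional swab and still turn some antigen results negative, or the reverse. With no text that ranks them, the primary result could be settled after both are known. A reader who takes the endpoint from 2.2 and the power from 4.1.2 would also attach 90% power to an endpoint for which none was calculated.

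**Working it through.** **1. Reproduce the plan's figure.** Inputs from 4.1.2: margin d = 3, true difference 0, one-sided 2.5%, power 90%, and the value 6 read as an SD (σ). Taken literally as a standard error, 6 would give power of about 7%, so the SD reading is the one that fits.

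n per group = 2(z₀.₉₇₅ + z₀.₉₀)²σ²/d² = 2 × (1.960 + 1.282)² × 36/9 = 84.06, rounded up to 85. Noncentral-t power at 85 per group is 90.0%. Two groups of 85 make 170, which matches the block size in 4.1.1.

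The margin is in cycles and the SD is that of Ct, so the 90% belongs to Ct.

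**2. Does the arithmetic identify the design?** No. For paired swabs with single-swab SD 6 and correlation ρ, the variance of the differences is 2 × 36 × (1 − ρ). At ρ = 0 this is 72, and the number of pairs is (1.960 + 1.282)² × 72/9 = 84.06, again 85. Two independent groups and uncorrelated pairs give the same number. Under neither reading does it apply to concordance.

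**3. Power of the planned paired Ct test.** Paired noncentral t, one-sided 2.5%, margin 3, true difference 0, 85 pairs with Ct observed on both swabs:

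| Meaning of 6 | SD of differences | Power |
|---|---|---|
| SD of within-participant differences | 6.00 | 99.5% |
| Single-swab SD, ρ = 0 | 8.49 | 89.7% |
| Single-swab SD, ρ = 0.2 | 7.59 | 95.0% |
| Single-swab SD, ρ = 0.5 | 6.00 | 99.5% |

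**4. What section 4 provides for each outcome.**

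| Element | Ct | Antigen concordance |
|---|---|---|
| Status in 2.2 | Secondary | Primary (only bullet) |
| Status in 4.1.3 | Primary | Not mentioned |
| Hypothesis and margin | Yes, -3 | None |
| Statistic and test | Mean difference; paired t or Wilcoxon | None |
| Reference swab | Named in each contrast | None; each participant has HCP NP and HCP OP+N |
| Sample size and power | 85 per group, 90% | None |

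**5. Can power for concordance be derived?** No. The documents give no statistic, margin, discordance rate or positivity. To show only that the Ct figure does not carry over, assume one possible statistic, the paired difference in proportion positive, with discordance ψ and margin m. For 90% power, pairs = ψ(1.960 + 1.282)²/m².

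- ψ = 0.05, m = 0.10: 53 pairs; 85 pairs give 98.5%.
- ψ = 0.20, m = 0.05: 841 pairs; 85 pairs give 17.6%.

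All four values are assumptions. The width of the range is the point.

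**The case against.** **Ct was plainly meant.** Section 2.2 itself describes Ct as a surrogate for sampling quality, and the background says the comparison will be made through Ct. On this view the bullet in 2.2 is a labelling slip. But the background also frames the open question as non-inferiority of supervised rapid antigen testing, and 2.3.2 collects swabs for antigen testing as well as for PCR. Both readings have support. Choosing Ct would still leave housekeeping or viral gene open: 4.1.4 treats Ct as a measure of viral load, while the background and 2.3.1 also refer to housekeeping genes.

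**Section 4.1.4 does contain a method for binary outcomes.** Logistic regression suits a positive/negative result. But it is there for stratification by confounders, names no outcome, and brings no margin or power. It does not fill the gap.

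Three stronger readings are tempting and are not supported:

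- *That 85 shows an independent-groups calculation wrongly applied to a paired test.* Step 2 gives the same 84.06 for uncorrelated pairs, and positive correlation only raises power.
- *That 4.1.2 claims 90% power for concordance.* It never mentions the primary endpoint. The link arises only when 4.1.2 is read together with 2.2.
- *That the trial is underpowered because viral Ct exists only in positives.* The documents give no positivity and do not fix the gene. If 10%, 20% or 30% were positive, about 8, 17 or 26 of 85 participants would contribute, with paired power of 23%, 49% or 69% at an SD of differences of 6, and 14%, 28% or 41% at 8.49. A higher correlation would raise these figures, and a housekeeping-gene Ct would not depend on positivity. This is a reason to state the assumption, not a finding about the trial.

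**Conclusion.** The contradiction stands on the current text and should be resolved before data are seen. Followed exactly, the plan has two different primary outcomes. The one named in 2.2 has no decision rule and no power. The one in 4.1.3 has both and is secondary in 2.2.

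The 85 per group and 90% are correct as a Ct calculation, provided that 6 is an SD. For the paired Ct test with complete Ct data, 85 pairs give 89.7% with uncorrelated single-swab SD 6 and 99.5% if 6 is the SD of differences, so the Ct figure is about right or conservative. For concordance no power exists, and none can be derived. The conclusion does not depend on any assumed positivity.

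**What to change.** Reconcile 2.2 with 4.1.2 to 4.1.4 before data are seen. The choice of route is the sponsor's.

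**(a) Make Ct primary in 2.2.**
- Name the gene and the contrast.
- State whether 6 is the SD of single swabs or of within-participant differences, and restate the power for the planned paired test.
- If the gene is viral, base the power on the expected number of positives, given as a stated assumption.
- Make concordance secondary: positive and negative percent agreement with exact confidence intervals against one named HCP swab. HCP OP+N is the like-for-like reference; NP can be reported separately.

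**(b) Keep concordance primary.**
- State the statistic, the named HCP reference swab, the margin or target, and the power or expected confidence-interval width.
- Relabel the Ct hypotheses in 4.1.3 as secondary.
- State in 4.1.2 that 85 per group and 90% power refer to the secondary Ct comparison.

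Under either route, give each hypothesis in 2.1 (GSS against HCP NP, GSS against HCP OP+N, GSS against USS) a primary or secondary status. Only GSS against HCP OP+N now appears in both 2.1 and 4.1.3.

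**Cost.** Text changes in 2.2 and section 4, and probably Ethics Committee approval as a substantial change under 5.4. The power or precision then stated may be less favourable than 90%. The fix itself does not require added enrolment.

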## 2.3 Project design

[figure not shown]
This is a single-center, randomized, controlled study at a Swiss test station.

### 2.3.1 Piloting

In order to assess the sampling quality by HCP or telemedically guided self-sampling, Ct values obtained in RT-PCR analysis of a COVID-19 assay, a housekeeping gene can be used for reference.

Hence, for the first part of the study, we will recruit 10 people in which we will perform an OP+N sampling at two-time points, 15 minutes apart, and compare the Ct values of these two values to calculate the standard deviation and see if the produced  $SD \cdot 1.96 / \sqrt{\text{Sample size}}$

equals the margin of error. Our 95% confidence interval (CI) will be standard deviation (SD) $\pm$  the margin of error.

Alternatively, we will pool confirmed RT-PCRs of two/three swab samples into one and spike them with SARS-CoV-2 standard. Next, we do as many repeats of the same sample on RT-PCR comparing housekeeper and SARS-CoV-2 genes. The advantage here is that we will have controlled starting biological material and the resultant SD / 95% CI will concern only the analytical and laboratory process variability. With the first approach, we will test SD of the swab procurer too, along with the interference coming from the analytical process (lab, instruments, sample storage).

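### The pilot's 95% CI appears to put a mean's margin of error around a standard deviation, so its upper limit is about 8 to 11% too low; a related label in the sample-size section is also wrong, with limited impact (minor)

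*Combined protocol and SAP*

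**What the plan says.** **Pilot (2.3.1 Piloting).** Ten people are sampled by the OP+N route twice, 15 minutes apart. Their Ct values are compared to calculate an SD. The team will then see whether SD × 1.96/√(sample size) equals the margin of error. The interval follows: "Our 95% confidence interval (CI) will be standard deviation (SD"), plus or minus that margin. An alternative pilot repeats the PCR on pooled, spiked material. There, the "resultant SD / 95% CI will concern only the analytical and laboratory process variability". The section does not say which SD is meant (of the 10 within-person differences, or pooled within person), or whether the sample size is 10 people or 20 swabs.

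**Sample size (4.1.2).** The section opens: "The SD of the mean of Ct values for RT-PCR analysis of multiple samples is not clearly defined in the literature". It then states that, with no true difference, "then 85 patients per group are required to be 90% sure that the lower limit of a one-sided 97.5% confidence interval" will lie above −3. The variability input is given as: "We, therefore, estimated a standard error of six that accounts for this variance". The non-inferiority limit is three.

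**Test (4.1.4).** The analysis is a paired t test, or a Wilcoxon test if the data are not normal.

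**The concern.** The quantity 1.96 × SD/√n measures the uncertainty of a mean. An SD estimated from few observations has a skewed sampling distribution, so its interval must reach further above the estimate than below it. A symmetric interval with a mean's half-width puts both limits too low. The upper limit matters more, because the pilot is there to show how variable swabbing and laboratory work can be, and an upper limit that is too low understates that.

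The sample-size section mixes the same two concepts. Six is the only variability assumption behind the size of the trial, and the section itself says that the literature is unclear on it. Anyone who wants to check six against data has to know whether it is an SD or a standard error, and of what.

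**Working it through.** **1. The plan's own sample size**

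Inputs, all from 4.1.2: margin 3, true difference 0, one-sided 2.5% (z = 1.960), power 90% (z = 1.2816), variability 6. For two independent groups:

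- n per group = 2 × (1.960 + 1.2816)² × 6²/3² = 84.06, rounded up to **85**.

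This matches the stated figure with six entered as the SD of single observations. The standard error of the difference at 85 per group is then 6 × √(2/85) = 0.92. Six is therefore an SD in this calculation, and the label is wrong.

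The same inputs with six as the SD of paired differences give (1.960 + 1.2816)² × 6²/3² = 42.03, so 43 pairs. The 85 is thus a two-independent-group figure, while 4.1.4 plans a paired test.

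**2. The pilot interval, read as an interval for the SD**

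Take the margin as 1.96 × SD/√n with n = 10:

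- 1 ± 1.96/√10 gives **0.38 to 1.62** times the SD.

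The standard interval for an SD under normality is SD × √(df/χ²(0.975, df)) to SD × √(df/χ²(0.025, df)):

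| SD used | df | Lower factor | Upper factor |
|---|---|---|---|
| SD of 10 within-person differences | 9 | √(9/19.023) = 0.69 | √(9/2.700) = 1.83 |
| Pooled within-person SD | 10 | √(10/20.483) = 0.70 | √(10/3.247) = 1.75 |

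Shortfall of the plan's upper limit:

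- 9 df: 1 − 1.620/1.826 = 11%
- 10 df: 1 − 1.620/1.755 = 8%

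The plan's interval lies wholly below the true SD with probability P(χ²(df) < df/1.620²):

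- 9 df: 5.5%
- 10 df: 4.5%

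The nominal rate is 2.5%. Misses on the other side are negligible (below 10⁻⁹), so total coverage is 94.5% or 95.5%.

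That closeness to 95% is an accident of n = 10. If the sample size is read as 20 swabs and the pooled SD (10 df) is used, the interval is 0.56 to 1.44 times the SD and coverage is 90.2%.

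**3. The pilot interval, read as a slip for a mean difference**

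The form of the margin is then right and only the multiplier is wrong. With 9 df the multiplier should be t = 2.262. Using 1.96 covers 91.8%. The miss rates in step 2 do not apply.

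**The case against.** **The margin is not cleanly defined.** The text says that the team will see if a quantity equals the margin of error. Strictly, that compares the quantity with a margin that is defined nowhere else. This stands as a caveat. If some other margin was intended, the figures in step 2 fall away. The section offers no other candidate, however, so treating the expression as the margin remains the most natural reading.

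**The sentence may be a slip for a mean.** It may be, but the section names no pilot mean, its stated aim is to calculate an SD, and the alternative pilot speaks of an SD with its CI. On the mean reading, too, 1.96 is wrong at n = 10.

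**Nothing depends on it.** This stands and sets the severity. Total coverage with n = 10 is near 95%. No section uses the pilot interval for a decision or to revise the sample size.

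**Stronger readings that the documents do not support.**

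- A reader might take the standard error of six literally and conclude that the trial is grossly underpowered. A standard error of the difference of six would give power Φ(3/6 − 1.96) = 7.2%. But 85 per group follows from the section's own inputs with six as an SD, so this figure describes no effect on the trial.
- A reader might infer that 85 is confirmed as the right number, or that 43 pairs would do. Neither follows. The documents do not say which SD six is, and they give no correlation between samples from the same person.
- The missing number of repeats for the spiked-sample option is only missing detail.

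**Conclusion.** The point holds as a minor one. On the readings that take the stated expression as the margin, the pilot's error bars are wrong. As an interval for an SD with n = 10, the upper limit is 11% too low (9 df) or 8% too low (10 df), and high-side misses are 5.5% or 4.5% instead of 2.5%. As an interval for a mean difference, the multiplier is 1.96 where 2.262 is needed. These figures assume approximately normal Ct values or differences.

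The standard-error label in 4.1.2 is a wording fault. With six as the per-observation SD in a comparison of two independent groups, 85 per group is reproduced, and relabelling does not change it. That statement does not settle whether 85 suits the paired analysis in 4.1.4.

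**What to change.** **2.3.1.** Name the SD and its degrees of freedom: 9 for the SD of the 10 within-person differences, 10 for the pooled within-person SD. Report it with the interval SD × √(df/χ²(0.975, df)) to SD × √(df/χ²(0.025, df)). Give any mean difference a t-based CI. State plainly what the margin of error is, or remove the comparison with it. If the spiked-sample option is used, state the number of repeats and take df = repeats − 1.

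**4.1.2.** Call six a standard deviation and say which one: of single Ct values, or of paired differences. Say also that 85 per group comes from a two-independent-group formula, and how that relates to the paired test in 4.1.4.

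**Cost.** One formula and a few words. No new data are needed, and the relabelling does not alter the stated sample size.
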